9.2 Determination of Sample Size

The sample size was calculated based on the objective of showing a greater proportion of patients experiencing an improvement in NRS score, from baseline to 12 months, when using CBMP in addition to the standard of care as compared to the standard of care alone. We assume that 25% of matched controls will experience an improvement in NRS score (O'Brien and Breivik, 2011). A sample size of 3600 patients using CBMP plus 3600 matched controls will provide at least 80% power to detect an increase in the proportion of patients experiencing a 28% improvement, using a two-sided z-test test for proportions with a Type I error rate of 5%. After adjusting for 10% non-evaluable rate and a 20% match failure rate, the sample size is 5000 CBMP patients plus 5000 matched controls.

Thus the null hypothesis $H_0: P=0.8$ is tested against the one-sided alternative $H_1: P>0.80$. Assuming that the expected pain reduction at 18 months for the treated subjects is $P_1=86\%$, a minimum sample size of 500 subjects for each type of chronic pain, with a total minimum number of 5000 subjects, is needed to design the study at 80% power, using a one-sided level 0.05 test for single proportion and the variance from the empirical estimate.

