5. STUDY OBJECTIVES

- The primary objective is to evaluate the effectiveness of the treatment regimen on reducing the average intensity of pain of subjects with chronic non-cancer pain compared to matched controls.
- The secondary objective is to evaluate the effectiveness of the treatment regimen on quality of life measurement, global impression of change, well-being, appetite, sleep scores and changes in concomitant medicine of chronic non cancer pain sufferers compared to matched controls.
- Safety and tolerability of the treatment regimen in chronic non-cancer pain subjects will also be assessed.

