9. STATISTICAL METHODS AND DETERMINATION OF SAMPLE SIZE

9.1 General considerations

The aim of the study is to evaluate whether a medical cannabis treatment in addition to standard of care is beneficial with regards to pain scores, quality of life measures, sleep scores, changes in concomitant medication use, subject's global impression of change and general wellbeing score, as well as being safe and tolerable. The study is a non-randomised, non-blinded, single arm study with comparisons being made against matched control database(s) where available and applicable.

There are many causes of chronic pain, which can be described as either neuropathic or non-neuropathic. In addition to those two main subtypes, there are 10 further subtypes which are as follows: systemic inflammatory disease, osteoarthritis, lower back pain, inflammatory bowel pain, neurogenic pain, post cancer pain, post trauma pain, psychogenic pain, genitourinary pain and vascular pain. These pain types will be recruited into both the CANPAIN cohort and matched cohorts.

The use of matched controls instead of a randomised control design is the best approach to studying medicinal cannabis due to the inherent difficulties of blinding trial subjects to the effects of cannabis. Protocol designs for the study of medicinal cannabis have been recently reviewed in a BMJ editorial (Freeman and Morgan 2019) which support the use study designs such as ours in the generation of evidence in medicinal cannabis use. Subjects in the active and control cohorts will be matched on a range of demographics, socio-economic, pain, and health related variables (see response to comment 1d). Certain covariates (such as gender) may be considered for exact matching if appropriate. Subjects will be matched using an optimal matching algorithm. For the primary analyses, a 1-1 matching algorithm will be used. At a predefined interval (12 months), a multiple regression analysis will be undertaken on subjects in the matched control cohort to assess which co-variables (e.g. categories of standard of care, pain type or location of pain). are important for the matching process with the CANPAIN cohort. Subgroups of special interest include type of pain, inclusion of gabapentinoids, age and gender. Subgroups of exploratory interest include but are not limited to, standard of care, site of pain and prior cannabis use. These will be fully defined in the SAP.

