9.5.1.1 Change in baseline pain NRS

The change in baseline pain NRS will be defined as the difference between chronic pain state at the beginning of the study versus the end of the study (after 3 years of treatment).

The primary analysis will be a difference analysis with comparison to appropriately selected matched controls. The endpoint will be tested using a two-sided z-test test to compare results between the prospectively enrolled treated participants and external matched controls. The impact of confounding factors will be reduced as much as possible by including values of important covariates in the model and by performing sub-analyses. Covariates included in the model will be selected based on:

- (1) Base line pain scores
- (2) Cannabis consumption experience and/or
- (3) Cause of chronic pain

A propensity score analysis may also be performed to match subjects between the treated and matched control groups. The propensity score is the probability of treatment assignment conditional on observed baseline characteristics. Propensity score matching entails forming

matched sets of treated and untreated participants who share a similar value of the propensity score (Rosenbaum PR & Rubin DB, 1983a and 1985).

Secondary measure outcome variables

Descriptive statistics will be presented for Quality of life changes, sleep NRS changes, Anxiety changes, confusion changes, dizziness changes, and changes in the use of concomitant medicines. Change from baseline to a number of analysis time points (including 12 months) will be assessed. Repeated measures analyses will be undertaken to allow for the evaluation of outcomes at any timepoint. In addition, multi-state modelling (MSM) will be undertaken to assess time-varying confounds. These will be described in detail in the SAP.

A comparison between treated subjects and matched control may be performed if similar endpoints are collected in both databases. Time to event analysis, multiple regression analysis for continuous and/or categorical outputs and/or propensity score analysis may be performed as appropriate.

To deal with missing data in subjects over the 3 year period, patterns of missingness will be evaluated including missing completely at random (MCAR), missing at random (MAR) or missing not at random (MNAR) will be assessed, this will be described in detail in the SAP.

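### The second sample-size calculation in section 9.2 does not give 500 per pain type (its stated inputs need about 207), has no control group, and is not reconciled with the two-group calculation before it

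*Protocol*

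**What the plan says.** All of this is in the draft CANPAIN protocol appended to the feasibility protocol as Appendix 1.

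Section 9.2 gives two justifications for 5000.

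- **First paragraph.** It compares two groups on the proportion improving "from baseline to 12 months, when using CBMP in addition to the standard of care as compared to the standard of care alone". The control rate is 25%, the test is two-sided at 5%, and 3600 per group is said to give at least 80% power for a figure of 28%. It ends: "After adjusting for 10% non-evaluable rate and a 20% match failure rate, the sample size is 5000 CBMP patients plus 5000 matched controls".
- **Second paragraph.** Presented as a consequence of the first, it sets a null of P = 0.80 against P > 0.80. "Assuming that the expected pain reduction at 18 months for the treated subjects is" 86%, it says that "a minimum sample size of 500 subjects for each type of chronic pain, with a total minimum number of 5000 subjects, is needed" for 80% power, "using a one-sided level 0.05 test for single proportion and the variance from the empirical estimate".

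Section 9.1 lists the pain types: besides neuropathic and non-neuropathic, "there are 10 further subtypes which are as follows". Section 5 gives the primary objective as "reducing the average intensity of pain of subjects with chronic non-cancer pain compared to matched controls". Section 9.5.1.1 says: "The endpoint will be tested using a two-sided z-test test to compare results between the prospectively enrolled treated participants and external matched controls".

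**The concern.** The second paragraph gives every input needed to check it, and 500 is well above what a one-sample test of a six-point difference near 0.80 should need at 80% power.

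It also cannot follow from the first paragraph. The number of groups, the sidedness, the time point and the assumed rates all change. What the 80% and 86% measure is not defined, and nothing links a null of 80% to a control rate of 25%. A test without a control term cannot support an objective and a primary test that are both comparisons with matched controls.

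At stake is whether 5000, the study's headline size, has one reproducible basis. As written, a reader cannot tell which calculation fixes it. Section 2 of the feasibility protocol says the work is meant to support a new ethics submission of CANPAIN, so the text is likely to be read again. The feasibility study's own minimum target of 100 does not depend on it.

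**Working it through.** **1. First calculation (reproduces).** Inputs from 9.2: control rate 0.25, treated rate read as 0.28, two-sided 5%, 80% power.

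- n per group = (1.96 + 0.842)² × (0.25 × 0.75 + 0.28 × 0.72) / 0.03² ≈ 3,393 (about 3,396 with pooled variance).
- Power at 3600 per group ≈ 82%, which agrees with at least 80%.
- Inflation: 3600 / (0.9 × 0.8) = 5000.

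The text does not say plainly that 28% is the treated rate. The other readings do not fit: a 28% relative increase (25% to 32%) needs about 649 per group, and a 28-point increase (25% to 53%) about 44.

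**2. Second calculation (does not reproduce).** Inputs from 9.2: P0 = 0.80, P1 = 0.86, difference 0.06, one-sided 0.05 (z = 1.645), 80% power (z = 0.842). The named variance is taken as P1(1 − P1) = 0.86 × 0.14 = 0.1204.

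- n = (1.645 + 0.842)² × 0.1204 / 0.06² = 206.8, so **207**.

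Other forms of the same one-sample, one-sided test at 80% power:

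| Form | n |
|---|---|
| Empirical variance (as stated) | 207 |
| Arcsine | 241 |
| Null variance under H0, alternative variance for power: ((1.645 × √0.16 + 0.842 × √0.1204)/0.06)² = 250.7 | 251 |
| The same, continuity-corrected | 268 |
| Null variance throughout | 275 |
| Exact binomial | 80% first reached at 249; held from 271 |
| Maximum variance 0.25 | about 429 |

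Adding the first paragraph's losses (dividing by 0.9 × 0.8 = 0.72) gives 207/0.72 ≈ 288 for the stated variance, and 275/0.72 ≈ 382 for null variance throughout.

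**3. What 500 would deliver.** Power is 98.7% (empirical variance), 97.6% (null variance under H0) or 96.7% (exact). At n = 500, 80% power corresponds to a treated rate of about 84.1% (empirical) or 84.3% (null variance), not 86%.

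**4. The two paragraphs side by side.**

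| | First | Second |
|---|---|---|
| Groups | Treated and matched controls | Treated only |
| Test | Two-sided 5% | One-sided 0.05 |
| Time point | 12 months | 18 months |
| Rates | 25% in controls; 28% | 80% null; 86% |
| Total | 5000 treated + 5000 controls | 5000 |

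The test in 9.5.1.1 is two-sided and against controls, so on both counts it matches only the first column.

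**5. Allowance for losses.** Ten subtypes × 500 = 5000, with nothing left for the section's own 10% non-evaluable rate. An even split would leave 5000 × 0.9 / 10 = 450 evaluable per type. That costs the stated test little (power 95% to 98%), but the text does not say whether 500 means enrolled or evaluable.

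**The case against.** **Scope.** The section belongs to an appended draft that has already been refused once, and the feasibility study has no inferential test. This limits the weight of the point. It does not remove it, because the draft is to be resubmitted.

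**Harmless direction.** The first calculation supports 5000 on its own, and the faulty one oversizes its test. Section 9.1 calls the analyses exploratory and offers results by pain type only if numbers permit. All of this is true. The fault is a wrong, conflicting justification, not a loss of power.

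**The variance wording is open to interpretation.** Taking it as 0.86 × 0.14 is a reading, so 207 should be seen beside 251 to 275. The overstatement runs from 500/275 ≈ 1.8 times to 500/207 ≈ 2.4 times. No one-sample form reaches 500.

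**The label may be wrong instead of the number.** A two-sample one-sided comparison of 0.80 with 0.86 needs about 484 per group, close to a rounded 500. The text says single proportion, so this is a guess about origin. If it is right, the paragraph still needs correcting.

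**Inferred readings.** The text can also be read with 28% as a responder threshold and the treated rate unstated. The treated-rate reading is chosen because it alone comes close to 3600, so the sponsor should confirm it. The multiplication by ten is likewise inferred. The allowance for losses is a minor remark and carries no weight in the conclusion.

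**Conclusion.** The concern holds. On its stated inputs the second calculation needs about 207 per pain type, and no more than 275 under the null, mixed, arcsine or exact one-sample forms. Even the maximum variance gives only about 429. At 500 the power is about 97% to 99%, not 80%.

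Separately, the paragraph conflicts with the calculation it claims to follow from, and it supports neither the matched-control objective in section 5 nor the two-sided test in 9.5.1.1.

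The conclusion assumes that the stated test (single proportion, one-sided) is the one intended. That the first calculation is sound assumes that 28% is the treated-group rate. This should be fixed before resubmission. Whether a 12-month responder endpoint fits the three-year change in 9.5.1.1 is a separate question, not settled here.

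**What to change.** **Preferred.** Delete the second paragraph of 9.2 and keep the two-group calculation as the sole basis for 5000, stating explicitly that 28% is the treated-group rate once the sponsor has confirmed this. Describe results by pain type through their precision. If the ten types were equal in size, there would be 5000 × 0.9 × 0.8 / 10 = 360 matched pairs per type. Treating the groups as independent, the 95% confidence interval half-width is then 1.96 × √((0.1875 + 0.2016)/360) ≈ 0.064, or about ±6.4 points. Both assumptions should be stated.

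**Alternative, if a single-group check by pain type is wanted.**

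- Name the variance and give the matching figure: 207 (empirical) or 251 (null variance under H0) for 80% power, or about 99% or 98% power at 500.
- Define the endpoint and give the source of the 80%.
- Say whether 500 is enrolled or evaluable.
- Reconcile the time point and rates with the first paragraph.
- Make clear that the check is not the primary comparison.

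Either change is wording only, adds no patients, and should be made before CANPAIN is resubmitted.

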9.3 Analysis Sets

Data from all subjects recruited to the study will be analysed using an Intention-to-treat (ITT) approach, therefore data will be included in the primary analysis irrespective of whether the stipulated dose regimen or all the study medicines were followed throughout the study. All participants who receive at least one dose of any of the study drugs will be included in the safety analysis set (SAF). A Per Protocol (PP) analysis may also be conducted, comprising those subjects who adhere to the regimen as per protocol, as defined by the database entry and excluding subjects with major protocol deviations.

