6.2 Discussion of study design and choice of control groups

The aim of the study is to evaluate whether the addition of medical cannabis to standard of care or at the completion of standard of care is beneficial with regards to pain scores, quality of life, quality of sleep and changes in the use of concomitant medication, as well as being safe and tolerable in subjects suffering from chronic non-cancer pain. The study will utilise a combination of patient reported outcomes and data from the NHS (chronic pain diagnosis, standard of care and health related laboratory tests) to provide a holistic evaluation of the CBMP treatment when combined with standard of care. The patient reported outcomes and NHS data will be transferred into an electronic health repository which will manage their day to day care, provide reports and alerts on the tolerability of the cannabis for each subject and will form the clinical trial database. The matched controls will exclude those potential participants who are consuming illicit cannabis, identified by drug screening. If participants are using illicit cannabis, they will be given the option to stop with a 3-week wash out period. If participants are not willing to cease, they will not be eligible for inclusion in the matched control cohort.

Controls

The analyses of effectiveness will be conducted through comparison with matched controls obtained from NHS sites established to enable data collection from consented subjects receiving standard of care only. Subjects who consent to have their data collected will be asked to provide essential demographic information, details on their chronic pain type, their standard of care and whether they are currently using medical cannabis to help with their pain. This information will be used to match the subject to subjects on the trial. The data collected in the match cohort will mirror the data collected from the CANPAIN minus tolerability data which will not be required.

The CANPAIN study will follow a pragmatic, real-world, 'all-comers' design with wide inclusion criteria, which is designed to result in a more representative sample of the target population and of the matched controls. Baseline characteristics of treated participants may still differ systematically from those of the matched control group and one must account for these systematic differences when estimating the effect of treatment on outcomes.

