6.5.1 Treatments administered

The treatment regimen will be as follows; a vaporised/inhaled medical cannabis strain (CBMP), namely Equipose 8-8 with a balanced 8% THC and 8% CBD content. Treatment is a full spectrum medical cannabis product presented as dried flower:

The cannabis will be delivered by a smart vaporiser device manufactured by Ryah. This is CE marked having passed CE-RED NB and IEC 60601 medical device safety tests. It is a temperature-controlled vaporiser with flow sensors that connects remotely with a smart-device. hosted application which collects dosing data from the vaporiser and patient reported outcomes, permitting further dosing only after completion of required data entry. The CBMP is placed in a prefilled cartridge which contains 250 mg of product. This cartridge is QR coded and must be read by the mobile application prior to loading into the vaporiser. Detailed instructions on how to use the vaporiser will be provided with each vaporiser and a UK-based technical helpline will be provided in case the subject needs to be assisted with vaporiser use.

Treatment is determined by the study Physicians based on the subject's medical history, their subtype of chronic pain and their experience with CBMP use. Study Physician will be given extensive guidance on state of the art of CBMP prescribing, ensuring that subjects can tolerate the CBMP and are not given a dose of THC that might cause excessive adverse events. All subjects will be prescribed an initial low dose of CBMP. Real-time evaluation of efficacy and tolerability will allow dose to be titrated appropriately.

Using the principles of universal precaution all subjects will start the protocol at a low dose. At the low dose the subject will commence with one 1 vape session (250 mg of cannabis) in the evening only. All subjects will progress to the higher dose at 1 month after baseline, unless

instructed not to by the study clinician, who will review how well the subject has tolerated the CBMP. The higher dose will consist of 2 vape sessions (250 mg total cannabis flos per cartridge) one in the morning and one in the evening.

6.5.2 Selection of doses in the study:

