9.4 Summary of treatment group comparability

Demographic and baseline characteristics and disease characteristics will be summarized and compared between the treated subjects and the subjects from matched control group(s) for the ITT and the PP populations.

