9.5 Methods of analysis

9.5.1 Effectiveness

The ITT Population will be used for all effectiveness analyses. Selected analyses may also be performed using the PP population. Effectiveness analyses will be presented for the overall populations and by subgroup of subjects (e.g. cause of chronic pain), as appropriate.

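### The optional per-protocol set selects on adherence to the CBMP regimen, a criterion with no counterpart in controls, so it should not be used for outcome contrasts with them

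*Protocol*

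**What the plan says.** All of this stands in the draft CANPAIN protocol appended to the feasibility protocol.

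- **Primary set.** Section 9.3 analyses by intention to treat: "data will be included in the primary analysis irrespective of whether the stipulated dose regimen or all the study medicines were followed throughout the study".
- **PP set.** The same section adds an optional set, "comprising those subjects who adhere to the regimen as per protocol", with adherence judged from database records. A second criterion is applied on top of this one: "excluding subjects with major protocol deviations".
- **What the regimen is.** Section 6.5.1 opens: "The treatment regimen will be as follows; a vaporised/inhaled medical cannabis strain (CBMP"). Section 6.5.3 monitors compliance with it through the study app and direct contact with subjects.
- **What controls receive.** Section 6.2 takes controls from NHS sites set up for "data collection from consented subjects receiving standard of care only". No adherence criterion is given for them.
- **Where the PP set is used.** Section 9.4 has demographic, baseline and disease characteristics "compared between the treated subjects and the subjects from matched control group(s) for the ITT and the PP populations". Section 9.5.1 then says: "Selected analyses may also be performed using the PP population".
- **What an effectiveness analysis is.** Section 9.5.1.1 makes the primary analysis a comparison with matched controls. It describes propensity scores as built on baseline characteristics.

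**The concern.** Adherence to CBMP is observed after treatment starts, and only treated patients can show it or fail to. Selecting on it in one cohort changes the mix of likely responders in that cohort and leaves the other as it was. Matching and propensity scores work on baseline variables, so they cannot undo a selection made later.

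The selection is plausibly linked to outcome. Section 6.4.6 treats perceived lack of response as a reason for withdrawal distinct from adverse events. Section 6.4.4 lists adverse events and non-compliance among the reasons for stopping study drug. A control who does badly on standard of care passes through no equivalent filter.

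At stake is a secondary estimate that could show a benefit where there is none, and that could then be cited as support for the ITT result.

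**Working it through.** **1. The yardstick in section 9.2.** The inputs are 25% of controls improving, 3600 evaluable per group and a two-sided 5% z-test. The 28% is read as the treated proportion, because the sentence is ambiguous.

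- Pooled standard error under no difference: √(2 × 0.265 × 0.735 / 3600) = 0.01040.
- Standard error under the alternative: √((0.25 × 0.75 + 0.28 × 0.72) / 3600) = 0.01040.
- Power: Φ((0.03 − 1.96 × 0.01040) / 0.01040) = 82.2%, consistent with the stated minimum of 80%.
- Inflation: 3600 / (0.9 × 0.8) = 5000, as stated.
- Reading 28% as a relative gain (25% to 32%) would need only 652 per group, so it does not fit 3600.

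On this reading the design difference is 3 points. The sample size is not affected by the present point.

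**2. Does the filter act on both cohorts?** The PP rule has two parts. The adherence part refers to a regimen that only treated patients receive, so it cannot apply to controls. The major-deviation part could apply to both. Controls consent and provide data, and section 6.2 bars those who will not stop illicit cannabis, so a control could have a major deviation. That does not mirror adherence to CBMP.

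**3. Bias with no true effect.** Let f be the share of treated patients removed as non-adherent, and g the response rate in adherers minus that in non-adherers. If the full treated cohort responds at 25%, as controls do:

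0.25 = (1 − f) × p(adherers) + f × (p(adherers) − g), so p(adherers) = 0.25 + f × g.

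The PP difference from controls is therefore f × g. The documents give neither quantity, so both are assumed over a range. Results are in percentage points:

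| Share removed | g = 5 | g = 10 | g = 15 |
|---|---|---|---|
| 10% | 0.5 | 1.0 | 1.5 |
| 20% | 1.0 | 2.0 | 3.0 |
| 30% | 1.5 | 3.0 | 4.5 |
| 40% | 2.0 | 4.0 | 6.0 |
| 50% | 2.5 | 5.0 | 7.5 |

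**4. What a nominal test would do.** Take 30% removed and a 10-point gap. The PP set then has 3600 × 0.7 = 2520 treated patients responding at 28%, against controls at 25%. A two-sided 5% test would reject in 74.6% of such null trials if all 3600 controls are kept. It would reject in 67.5% if the partners of excluded patients are dropped as well. Dropping partners costs precision but leaves the expected 3-point bias, because controls are matched on baseline variables and not on adherence.

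**The case against.** The strongest reply is that the protocol never states a PP outcome comparison with controls. Section 9.4 is a balance table without outcomes, so losing non-responders cannot create a false effect in it. Section 9.5.1 is permissive and does not mention controls. PP is optional, ITT is primary, section 9.1 calls the analyses exploratory with p-values read descriptively, and the use of the control database is left to the SAP. Section 6.5.3 also expects good compliance. All of this stands, and it limits the weight. It does not remove the point. The protocol itself fixes a definition that can apply to one cohort only, pairs that set with controls in 9.4, and allows effectiveness analyses in it when the stated form of such an analysis is a comparison with controls. A SAP that follows this wording inherits the asymmetry.

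A reader might infer more than the text supports:

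- **That the rule can remove treated patients only.** This holds for the adherence part, not for the major-deviation part.
- **That the 1-1 pairs are broken.** Section 9.1 sets 1-1 matching for the primary analyses. Nothing says whether PP pairs would be kept, dropped or re-matched.
- **That the PP result must favour CBMP.** Section 6.4.4 also lists pregnancy, use of other cannabis and non-compliance with procedures, and section 6.5.1 blocks further dosing until data are entered. Upward bias is plausible, but its direction depends on g being positive.
- **That the bias is around 6 points or more.** If 30% are removed and only 10% of them improved, the PP rate is (0.25 − 0.30 × 0.10) / 0.70 = 31.4%, a 6.4-point bias. That assumes a gap of 31.4 − 10 = 21.4 points, which nothing in the documents supports.

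**Conclusion.** The point holds in a limited form. Any PP outcome contrast with controls would compare treated patients selected after baseline on adherence with controls not so selected. It would tend to favour CBMP if non-adherers respond less often. With no true effect the bias is f × g, roughly 0.5 to 7.5 points over the assumed ranges, and 3 points at 30% removed with a 10-point gap. That equals the design difference if 28% in section 9.2 is the treated rate. If compliance is as good as section 6.5.3 expects, the bias sits at the low end. The adherence shares and gaps are assumptions; the asymmetry of the definition is not. This is a cheap improvement to the draft CANPAIN protocol. It does not threaten the ITT analysis or any objective of the feasibility study.

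**What to change.** State in sections 9.3 and 9.5.1 that PP effectiveness results describe the treated cohort only and are not contrasted with controls. If an adherence-based contrast is wanted, specify adherence weighting on the full matched cohort, labelled as a sensitivity analysis, and name the assumption it needs: that the variables driving both adherence and outcome are measured. The section 9.4 baseline table for the PP set can stay as a description of how adherers differ.

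Defining how controls enter the PP set would be a partial alternative, but adherence to standard of care is a different filter and would not restore comparability.

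The cost is a few sentences and the loss of one optional contrast. Sample size, data collection and the primary analysis do not change.
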